8.5.3. Safety Monitoring Rules for Platelet Count Results

Platelet count will be monitored at least every 4 weeks during the Treatment and Post-Treatment Periods as per visit schedule in Appendix A.

The Investigator or the designee should review all PLT count results within 48 hours of receipt. Any unreportable PLT count result must be rechecked ideally within 7 days and determined not to have met a stopping rule before dosing can continue.

Actions to be taken in the event of reduced PLT count are shown in Table 2.

Protocol

Platelet count (K/mm³)	Dosing	Monitoring frequency
≥ 125	No action	At least every 4 weeks.
> 100 to < 125	Dosing every 4 (Cohort A) or 8 (Cohort B) weeks should be continued.	At least every 2 weeks until 2 successive values > 125K/mm ³ .
$\geq 75 \text{ to} \leq 100$	Dosing every 4 (Cohort A) or 8 (Cohort B) weeks may be continued if approved by the Sponsor Medical Monitor.	Every week until 2 successive values > 100K/mm³. Consider more frequent monitoring if additional risk factors for bleeding are present.*
≥ 50 to < 75	Pause dosing. When PLT count returns to > 100K/mm ³ , restart dosing only if approved by the Sponsor Medical Monitor.	Twice weekly until 2 successive values > 75K/mm³, then weekly until 2 successive values > 100K/mm³. Consider more frequent monitoring if additional risk factors for bleeding are present.*
≥ 25 to < 50	Permanently discontinue Study Drug. Consider corticosteroids if additional risk factors for bleeding are present.**	Twice weekly until 2 successive values > 75K/mm³, then weekly until 2 successive values > 100/mm9. Consider more frequent monitoring if additional risk factors for bleeding are present.*
< 25	Permanently discontinue Study Drug. Corticosteroids strongly recommended.**	Daily until 2 successive values > 25K/mm³, then twice weekly until 2 successive values > 75K/mm³, then weekly until 2 successive values > 100K/mm³. Consider more frequent monitoring if additional risk factors for bleeding are present.*

^{*} The suitability of the patient for interrupted and/or continued dosing will be determined by the Investigator or designee in consultation with the Medical Monitor and will be based on factors such as the original rate of decline in the patient's PLT count, whether any bleeding events were experienced by the patient, and the speed of recovery of PLT count after interruption of dosing.

There will be lab alerts for PLT values under 100,000/mm³.

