9.3.4. Adverse Event of Special Interest (AESI)

For the purpose of this study, severe reductions in PLT count < 50,000/mm³ accompanied by a MB event or CRNMB event, or PLT count of < 25,000/mm³ independent of a MB or CRNMB event, are considered as AEs of special interest (AESIs) and are subject to 15-day expedited reporting by the Sponsor to the regulatory agencies.

Amendment 2 12 July 2022

Adverse events of special interest are required to be reported by the Investigator or designee to the Sponsor immediately, within 24 hours of the Study Center's first knowledge of the event, for expedited reporting to Regulatory Authorities.

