For platelet (K/mm³), the number and percentage of patients falling in each of the following categories based on the confirmed results (both central and local lab data will be used) will be tabulated by treatment group for ≥ 125 , ≥ 100 to < 125, ≥ 75 to ≤ 100 , ≥ 50 to < 75, ≥ 25 to < 50, < 25.

A confirmed value is based on a consecutive lab value within 7 days. If that value is in the same or worse category the initial value is confirmed. If the consecutive value is in a better category, then the initial value is confirmed using the consecutive value category. If there is no retest within 7 days, then the initial value is presumed confirmed. If there are multiple results on the same day, no matter from the same lab vendor or different lab vendors, then the worst value will be utilized in the analysis.

Laboratory data will be presented in by-patient listings.

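### The platelet table uses confirmed values only, so an isolated count below 25,000/mm³ that is an AESI can be absent from its < 25 row; a count of 100 also fits two categories

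*Combined protocol and SAP*

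**What the plan says.** SAP 4.10.4 tabulates by treatment group "the number and percentage of patients falling in each of the following categories based on the confirmed results", using central and local laboratory data. Confirmation works as follows:

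- Window: "A confirmed value is based on a consecutive lab value within 7 days".
- Retest no better: "If that value is in the same or worse category the initial value is confirmed".
- Retest better: "If the consecutive value is in a better category, then the initial value is confirmed using the consecutive value category".
- No retest: "If there is no retest within 7 days, then the initial value is presumed confirmed".
- Several results on one day: the lowest counts.

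Protocol 9.3.4 defines two platelet AESIs. One is a count below 50,000/mm³ together with major or clinically relevant non-major bleeding. The other needs no bleeding: "or PLT count of < 25,000/mm³ independent of a MB or CRNMB event, are considered as AEs of special interest (AESIs". Sites report both within 24 hours, and the sponsor expedites them within 15 days. Neither definition mentions a confirmatory sample.

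For counts below 25 K/mm³, protocol 8.5.3 (Table 2) sets the monitoring frequency as "Daily until 2 successive values > 25K/mm³", with less frequent checks after that.

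The SAP's platelet categories include "≥ 100 to < 125, ≥ 75 to ≤ 100". The corresponding upper row of protocol Table 2 starts strictly above 100.

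**The concern.** The table and the AESI definition share the 25 K/mm³ threshold but treat the same laboratory value differently. The AESI is triggered by one count. The table lets the next count overrule it, and always towards the milder category when the two differ in that direction. A reader who compares the < 25 row with the expedited reports could find a patient in one and not in the other, with no planned table to explain the difference.

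The trial has dosing and monitoring rules tied to these platelet categories, so this is a table that safety readers will consult. The groups are small enough that one patient is visible in the percentages.

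The overlap at 100 is a separate and simpler matter. As written, the categories are not mutually exclusive, and a programmer has to guess where that value goes.

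**Working it through.** The plan states no figure to reproduce here, so the check applies the rule literally and then looks for other planned output that would show the same patients.

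**1. The rule.** For each day, take the lowest count and its category. If the next count falls within 7 days and in a better category, use that category; otherwise keep the initial one. Place the patient in the worst resulting category. This last step is an assumption, because the SAP does not spell it out. It does not affect whether a patient has any entry in the < 25 row.

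**2. The rule applied to eight hypothetical series** (K/mm³; assumed values, each containing a count of 20):

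| Series | Worst raw category | Worst confirmed category |
|---|---|---|
| 20, then 30 next day | < 25 | 25 to < 50 |
| 20, then 130 next day | < 25 | ≥ 125 |
| 40, 20, 40 on successive days | < 25 | 25 to < 50 |
| 20 and 30 on one day, 30 next day | < 25 | 25 to < 50 |
| 20, 22, 30 daily | < 25 | < 25 |
| 20, 15, 30 daily | < 25 | < 25 |
| 20, no retest within 7 days | < 25 | < 25 |
| 20 and 30 on one day, no later retest within 7 days | < 25 | < 25 |

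All eight meet the AESI threshold on raw counts, and four stay in the < 25 row. The series were chosen to exercise each branch of the rule, so 4 of 8 is not an estimate of frequency. The pattern is that a patient leaves the row only if every count below 25 is followed within 7 days by one of 25 or more.

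**3. Whether a retest is to be expected.** Table 2 asks for daily counts below 25, so a next value inside the 7-day window is the planned course. The presumed-confirmed fallback should seldom be needed when the protocol is followed.

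**4. Other planned output.**

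- Adverse event tables (SAP 4.10.2) would carry the event once reported. Severity does not isolate it, because protocol Appendix D grades every platelet count below 100,000/mm³ as severe.
- SAP 4.10.3 covers injection-site reactions, flu-like reactions and bleeding. It has no AESI table.
- By-visit hematology summaries include a minimum. They use central laboratory data only (SAP 4.10.4) and, within a visit window, the value nearest the scheduled date (SAP 4.2.3). The lowest count need not appear.
- Listings show every laboratory value.
- Protocol 10.6.2 promises tables and/or narratives of significant adverse events and a count of patients with laboratory abnormalities. The SAP does not turn this into a table of AESIs or of worst unconfirmed counts.

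**5. Size of one displaced patient.** At the group sizes in the plain-language summary: 1/45 = 2.2%, 1/23 = 4.3%, 1/22 = 4.5%. At the planned sizes in protocol 10.2: 1/42 = 2.4%, 1/21 = 4.8%.

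**6. The boundary.** A count of 100 satisfies both 100 ≤ x < 125 and 75 ≤ x ≤ 100. Under Table 2 it satisfies only the second, because the upper row requires x > 100.

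**The case against.** Confirmation is a defensible choice. Protocol 8.5 requires results that meet monitoring criteria to be confirmed on a new specimen, ideally within 3 days. The protocol's list of tables describes Table 2 as applying to confirmed low counts. The SAP uses confirmed values for ALT and AST as well, and protocol 6.2.1 anticipates uninterpretable platelet specimens such as clumped ones. The rule also has conservative features: unretested values count as confirmed, the worst same-day value is used, and local results are included. An expedited-reporting trigger and a summary table serve different purposes, so a difference between them is not in itself a contradiction. Protocol 2.5.1 reports no platelet signal in the earlier studies.

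All of this stands, and it is why the confirmed table should be kept. It does not fill the gap: the protocol attaches AESI status to an unconfirmed count, and no planned table shows unconfirmed counts at that threshold.

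A reader might go further and infer that this is the only planned summary of severe platelet falls. The documents do not support that. The adverse event tables, by-visit minima and listings all carry relevant information; what is missing is the dedicated view.

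**Conclusion.** The point holds in a limited form. The rule can remove a patient with an isolated count below 25 K/mm³ from the < 25 row, although that count is an AESI. The case is not lost from the study record. Each such patient changes the row by 2.2 to 4.5 percentage points at the reported group sizes. This assumes the rule is applied to each count in turn, as written. The documents do not show that any patient had such a count.

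A reader might also infer that a predictable share of AESI counts would disappear, or that treatment or stopping the drug would nearly always lift the next value. Neither follows. The documents give no figure for specimen-to-specimen platelet variability or for speed of recovery. The chance that one retest exceeds 25 is not the chance of leaving the row, since any two successive counts below 25 (within 7 days) keep the patient in. For a first low count, the deciding value is the first retest, which may precede any effect of treatment.

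The added table is a cheap improvement. The boundary at 100 is wrong as written and needs correcting regardless.

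**What to change.** Keep the confirmed table. Beside it, add the worst unconfirmed post-baseline platelet count per patient, by treatment group and in the same categories. Exclude only specimens flagged as uninterpretable, and flag counts that meet the AESI definition in protocol 9.3.4. Change the lower limit of the SAP's second category so that it reads > 100 to < 125, matching protocol Table 2. SAP section 1 allows additional analyses after database lock to be described in an addendum or in the study report.

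The cost is one extra table and one corrected boundary. Isolated spurious low values will appear in the new table and may need a footnote. No monitoring or dosing rule is affected.

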4.10.5. Vital Signs, Physical Findings and Other Observations Related to Safety

4.10.5.1. Vital Signs

Vital signs will include heart rate, respiratory rate, body temperature, systolic and diastolic blood pressure and pulse pressure. Summary tables will be created to present the descriptive statistics (n, mean, standard error, standard deviation, median, 25th percentile, 75th percentile, minimum, and maximum) for vital sign values, weight, and BMI as well as the change and percent change from baseline at each analysis visits.

4.10.5.2. Physical Examinations

Adverse changes in physical examinations that are deemed clinically significant by the Investigator will be classified as AEs. All physical examination data will be provided in a by-patient listing. Per Study Protocol Amendment 2 (UK only), additionally, assessments of growth development and sexual maturity (i.e., Tanner Staging) for adolescent patients (12-17 years) will be provided in a by-patient listing.

4.10.5.3. 12-Lead Electrocardiograms (ECG)

Safety 12-lead ECG data will include Ventricular Rate, PR Interval, RR Interval, QRS Duration, QTc, QTcF (QT corrected using the Fridericia's formula), QTcB (QT corrected using the Bazett's formula), and Overall interpretation. QTcF and QTcB will be calculated based on the patient's reportable ECG data at each time point using the formula described below:

TP-GDO-WW-016-08 CONFIDENTIAL Project Document Version No. 2.0
Effective Date: 26 Nov 19 Project Document Effective Date: 13 Dec 2023
Related to: SOP-GDO-WW-019 Page 43 of 61

QTcF = QT / (RR)
$$^{1/3}$$
, where RR = 60/VR
QTcB = QT / (RR) $^{1/2}$, where RR = 60/VR

For the continuous variables above, descriptive statistics (n, mean, standard error, standard deviation, median, 25th percentile, 75th percentile, minimum and maximum) of the results at each analysis visit, as well as the changes and percent changes from Baseline to each study visit, will be presented in summary tables; for the categorical responses to overall interpretation, the results and the associated findings at each visit will be summarized by counts and percentages. In the case when triplicate results are collected, for the continuous variables, average of triplicate results will be derived before generating the descriptive summary; for the categorical responses, the worst of triplicate results will be choosing for the descriptive summary.

All the ECG data collected will be listed.

4.10.6. Data Monitoring

4.10.6.1. Safety Data Monitoring

Ionis (or designee) is responsible for processing all reported AEs. All serious adverse events (SAEs), reported to Ionis (or designee), are reviewed according to standard operating procedures. The medical monitor will review all AEs and SAEs on an ongoing basis throughout the study. Ionis (or designee) will prepare and submit safety reports to the health authorities worldwide in accordance with local requirements. If it becomes necessary to communicate new safety information, Ionis (or designee) will also prepare a safety notification letter and transmit it to study site.

4.10.6.2. Data and Safety Monitoring Board

An independent Data and Safety Monitoring Board (DSMB) will be established to monitor the overall safe conduct of the study. Based on its ongoing assessment of the safety and tolerability of ISIS 721744, the DSMB will provide recommendations to the Sponsor for modifying, stopping or continuing the study as planned. Details on the safety assessments, frequency of review, meeting schedules, and controlled access to unblinded data are outlined in the DSMB Charter.

4.11. Pharmacokinetics

Plasma concentrations of ISIS 721744 (measured as total full-length oligonucleotides or ISIS 721744-equivalent, i.e., ISIS 721744-eq, including fully conjugated, partially conjugated, and unconjugated ISIS 721744, along with the scheduled (nominal) and actual sampling times (i.e., time from subcutaneous [SC] dosing) will be listed for each evaluable patient by treatment, actual dose, cohort, gender, body weight, age, subject IM status, and study day. Plasma concentrations below the lower limit of quantification (LLOQ) will be indicated by "BLQ". Percent differences between nominal and actual dose, as well as between scheduled and actual sampling times will also be listed for all patients.

For all patients administered with ISIS 721744, ISIS 721744 plasma trough, 2 hours post-dose concentrations after the first and last dose and post-treatment concentrations will be summarized

TP-GDO-WW-016-08 CONFIDENTIAL Project Document Version No. 2.0 Effective Date: 26 Nov 19 Project Document Effective Date: 13 Dec 2023 Related to: SOP-GDO-WW-019 Page 44 of 61

using descriptive statistics by treatment, dose, cohort, study day, and scheduled time point, without and with age group stratification (12 to < 18-year-old and ≥ 18-year-old patients), without and with stratification by subject Anti-Drug Antibody (ADA) status overall (see Section 4.12.2). For the purpose of calculating typical summary descriptive statistics (n, mean, SEM/SD, %CV, geometric mean, geometric %CV, median, minimum, and maximum) for plasma concentrations, all BLQ values will be set to zero. Mean plasma concentrations that are below the LLOQ will be presented as BLQ, and the SD, SEM/SD, %CV, and geometric %CV will be reported as not applicable (NA). Other stratifications may also be performed if deemed warranted. Samples will be excluded from descriptive statistics if there are large deviations between scheduled and actual sampling times (percent difference between scheduled and actual sampling time greater than 30%), or large deviations between actual dose and nominal dose (percent difference between nominal and actual dose greater than 30%). Any samples excluded from the summary descriptive statistics, if deemed necessary, will be listed separately along with the reason for exclusion.

Population PK, PK/PD or exposure-response analysis may be performed using the PK and PD data from this study, and/or combined with other clinical study data and reported separately. If appliable, details of these analyses will be presented in a separate analysis plan.

4.12. Immunogenicity (IM) Analysis

Samples collected for IM assessment at baseline (Day 1 pre-dose), during treatment and post-treatment follow-up period including early termination samples will be analyzed for anti-ISIS 721744 antibodies (ADA).

4.12.1. Sample Level ADA Data

An evaluable sample will be designated 'Positive' based on both positive screening and confirmation assay results (i.e., confirmed positive result), and otherwise will be deemed 'Negative'. Sample ADA results (screen positive/negative, confirmed positive/negative or unevaluable, and when applicable, titer of anti-ISIS 721744 antibodies) before, during, and after treatment with study drug (ISIS 721744 or placebo) (sample ADA status) will be listed by treatment, dose, cohort, and day of collection.

The sample ADA incidence (number) and incidence rate (percent) at each evaluated study time point will be determined and appropriately summarized by treatment, dose, and cohort as the total number of and percentage of evaluated subjects with sample ADA negative, positive, and unknown status. Furthermore, titer over time will be also appropriately summarized (using descriptive statistics) as median, quartiles (25% and 75%), and range by treatment, dose, and cohort. Summarization of ADA incidence, incidence rate and titer by age group (12 to \leq 18-year-old and \geq 18-year-old patients) may also be reported.

4.12.2. Subject Level ADA Data

Subject ADA status overall (ADASTAT) will be defined as 'Positive' status if they have at least one confirmed positive sample result at any time during the treatment or post-treatment evaluation periods; 'Negative' status if all evaluated ADA sample results during the treatment

TP-GDO-WW-016-08 CONFIDENTIAL Project Document Version No. 2.0 Effective Date: 26 Nov 19 Project Document Effective Date: 13 Dec 2023 Related to: SOP-GDO-WW-019 Page 45 of 61

and post-treatment evaluation periods are ADA negative and they have at least one evaluable ADA result collected post study drug treatment. Otherwise, a study subject will be assigned 'Unknown' ADA status.

Furthermore, subjects with positive overall ADA status will be further classified into different ADA types (ADATYPE) based on their baseline ADA status and change in ADA titer post-treatment as described below:

- Treatment-Emergent ADA: sum of treatment-induced ADA and treatment-boosted ADA as described below:
 - Treatment-Induced ADA: ADA developed de novo (seroconversion) following biologic drug administration (i.e., formation of ADA any time after the initial drug administration in a subject without pre-existing ADA, i.e., baseline negative ADA)
 - O Treatment-Boosted ADA: pre-existing ADA that were boosted to a higher level following biologic drug administration (i.e., any time after the initial drug administration the ADA titer is greater than the baseline titer by a factor of 8-fold or more
- Treatment-Unaffected ADA: pre-existing ADA that were not affected (boosted) following biologic drug administration (i.e., any time after the initial drug administration the ADA titer is 4-fold or less)
- ADATYPE would be not applicable (NA) if the subject overall ADA status is negative.

Other subject level IM parameters to be calculated/defined may include but not limited to:

- Subject ADA Status at Baseline (ADASTATB): "Positive" if the subject has Week 1 Day 1 pre-dose sample (baseline) tested as confirmed positive; "Negative" if the subject has Week 1 Day 1 pre-dose sample (baseline) tested as confirmed negative; "Unknown" if the subject has Week 1 Day 1 pre-dose sample (baseline) unevaluable.
- Onset of ADA (TFSTADA): i.e., the first day ADA positive sample observed, will be calculated by: the date of first sample has "positive" sample IM status first dose date +1
- Last Positive ADA Study Day (TLSTADA): defined as the last positive ADA sample observed from the start of study drug treatment and will be calculated by: the date of last sample has "positive" sample IM status first dose date +1
- Last IM Sampling Study Day (TLSTSAMP): defined as the last ADA sample collected from the start of study drug treatment and will be calculated by: the date of last sample collected first dose date +1
- Peak titer (PEAKTIT): the highest titer observed for the subject
- Time to peak titer (TPEAKTIT): the time to reach peak titer will be calculated by: the date of first peak titer observed- first dose date +1

TP-GDO-WW-016-08 CONFIDENTIAL Project Document Version No. 2.0 Effective Date: 26 Nov 19 Project Document Effective Date: 13 Dec 2023 Related to: SOP-GDO-WW-019 Page 46 of 61

- Total number of ADA Positive Samples (NOPOSAMP): the total number of ADA samples being confirmed positive for the subject
- Total number of ADA Samples evaluated (NOADASAMT): the total number of ADA samples being collected and analyzed successfully with reportable results for the subject

Lastly, subjects with positive ADA status may further be classified as being transient or persistent ADA response, if there are sufficient number of subjects with transient ADA status. Transient and persistent ADA definitions are defined below and based on:

Transient ADA response:

- Treatment-induced ADA detected only at one sampling time point during the treatment or follow-up observation period (excluding the last sampling time point, which will be considered persistent unless shown to be undetectable at a later time) or
- Treatment-induced ADA detected at two or more sampling time points during the treatment (including follow-up period if any), where the first and last ADA-positive samples (irrespective of any negative samples in between) are separated by a period less than 16 weeks, and the subject's last sampling time point is ADA-negative.

Persistent ADA response:

- Treatment-induced ADA detected at 2 or more sampling time points during the treatment (including follow-up period if any), where the first and last ADA-positive samples (irrespective of any negative samples in between) are separated by a period of 16 weeks or longer or
- Treatment-induced ADA detected only at the last sampling time point of the study treatment period or at a sampling time point with less than 16 weeks before an ADA-negative last sample.

The subject level ADA prevalence, incidence, and positive ADA response being transient or persistent (if applicable) will be calculated as the number and the proportion (percent) of the study population during the study period by treatment, dose, and cohort. Subject level IM parameters (as described above) will be listed by treatment, dose, and cohort for all evaluable subjects, and also appropriately summarized (using descriptive statistics) as median, quartiles (25% and 75%), and range by treatment, dose, and cohort. Summarization of subject level ADA response and IM parameters by age group (12 to < 18-year-old and ≥ 18-year-old patients) may also be reported.

